The aim of the current study is to search for a diagnostic test which might predict microangiopathic hemolytic anemia and persistent HELLP syndrome from cases who initially diagnosed as HELLP syndrome in order to start PEX/ FFP which might decrease the maternal mortality rate at Ain Shams maternity hospital

Patients and Methods

Study Design:

- o diagnostic test accuracy. (pilot study)

Study Setting:

- o Ain Shams University Maternity Hospital from January 2015 to December 2015.
- o Intensive Care Unit , Wards, Labour ward at Ain Shams University Maternity Hospital and Hematology Unit and Clinical Pathology Unit at Ain Shams University.

Study Population:

A total of 100 women with an initial diagnosis of HELLP syndrome will be recruited in the study.

Blood sample taken within 12hrs peripartum and patients will be followed up 48hrs after delivery and subdivided in to 2 groups according to improvement or deterioration after 48hrs after delivery .

Inclusion criteria :

- o Gestational age more than 20 weeks.
- o Age from 18 to 40 years old.
- o Fulfilled criteria for the diagnosis of severe preeclampsia.
- o Fulfilled criteria for the diagnosis of HELLP syndrome.

Diagnostic criteria for severe preeclampsia(one of the following):

- Blood pressure of 160 mm Hg systolic or higher or 110 mm Hg diastolic or higher on two occasions at least 6 hours apart while the patient is on bed rest (unless antihypertensive therapy is initiated before this time).
- New onset Cerebral or visual disturbances.
- Pulmonary edema or cyanosis.
- Severe persistent epigastric or right upper-quadrant pain unresponsive to medication and not accounted for by alternative diagnosis, or both.
- Impaired liver function as indicated by abnormally elevated blood concentration of liver enzymes (to twice normal concentration).
- Thrombocytopenia (platelet count less than 100, 000 per microliter. *(ACOG., 2013)*

Diagnostic criteria for HELLP syndrome:

- Hemolysis documented by an increased LDH level and progressive anemia .
- Hepatic dysfunction documented by an LDH level >600 IU/L, elevated liver enzymes documented by AST >40 IU/L, ALT >40 IU/L, or both .

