- Thrombocytopenia documented by a platelet nadir less than 150, 000 cells/mm³. Thrombocytopenia is subclassified as class one HELLP syndrome: platelet nadir \leq 50, 000 cells/mm³, class two HELLP syndrome: platelet nadir \leq 100, 000 cells/mm³, or class three HELLP syndrome: platelet nadir \leq 150, 000 cells/mm³.*(Martin ., et al 1999)* .

Anticipation of Microangiopathic Hemolytic Anemia:

Thrombotic thrombocytopenic purpura-hemolytic uremic syndrome should be considered in all pregnant women with severe thrombocytopenia, severe anemia, and elevated lactate dehydrogenase enzyme (*Stella ., et al 2009*).

Methodology:

All included women will be subjected to the following:

- o History taking and consent
- o Consent form:
 - o Patient name:
 - o Hospital number:
 - o Information to the participant:
 - o The procedure
 - 1. The results of your blood results and hospital data will be used in this clinical trial.
 - 2. An extra blood sample will be withdrawn at the time of diagnosis which is a simple procedure with no known complications.
 - 3. All your data and blood results, will saved confidentially and it will appear as a number in the results.
 - 4. The results of these investigation will not affect your management plan.

- o General, abdominal and local examination.

Laboratory test:

complete blood count, using EDTA-anticoagulated peripheral blood sample, for concentration and platelet counts.

Peripheral blood smears will be taken within 12hrs peripartum and prepared within two hours of blood collection using the EDTA-anticoagulated peripheral blood sample. The blood smear then spread, air-dried, and fixed and stained according to standard procedures with panoptical stains Romanowsky stain as reported by (*International Council for Standardization in Hematology; 1984*).

Schistocytes are fragments of red blood cells (RBCs) produced by extrinsic mechanical damage within the circulation. The detection of schistocytes is an important morphological clue to the diagnosis of thrombotic microangiopathic anemia (TMA). Reporting criteria between different laboratories, however, are not uniform, owing to variability of shape and nature of fragments, as well as subjectivity and heterogeneity in their morphological assessment. Lack of standardization may lead to inconsistency or misdiagnosis, thereby affecting treatment and clinical outcome. The Schistocyte Working Group of the

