Association between the Quantitative Assessment of Schistocytes in Peripheral Blood Smear and Prognosis of Patient Initially Diagnosed as HELLP Syndrome (Study results)

[figure not shown]
[figure not shown]

Figure-26 Box-Plot Chart showing Difference between Women who Deteriorated Postpartum and Women who did

not regarding Gestational Age .

There were no significant differences between women who deteriorated postpartum and women who did not regarding the initial values of systolic blood pressure, diastolic blood pressure, albuminuria, hemoglobin concentration, platelet count or serum creatinine. The initial levels of serum ALT, AST and total bilirubin were, however, significantly, higher in women who deteriorated postpartum (table-9, figures 27-34).

Table-9 Difference between Women who Deteriorated Postpartum and Women who did not regarding Initial Clinical and Laboratory Data .

Initial Data	Women who Deteriorated Postpartum (n=25)	Women who Did not Deteriorate Postpartum (n=75)	P
Systolic Blood Pressure (mm Hg) Range	170 – 190	170 – 240	0.366*

Association between the Quantitative Assessment of Schistocytes in Peripheral Blood Smear and Prognosis of Patient Initially Diagnosed as HELLP Syndrome (Study results)

Median (IQR)	180 (170 – 190)	180 (170 – 190)	NS
Diastolic Blood Pressure (mm Hg)			
Range	100 – 130	90 – 150	0.123*
Median (IQR)	100 (100 – 110)	110 (100 – 120)	NS
Albuminuria			
3+	13 (52%)	28 (37.7%)	
4+	5 (20%)	27 (36%)	0.287**
5+	7 (28%)	20 (26.7%)	NS
Hb Concentration (g/dl)			
Range	6.6 – 9.5	6.5 – 9.8	0.747*
Median (IQR)	8.6 (7.5 – 9.05)	8.7 (8 – 9)	NS
Platelet Count (x 10,000 per mm³)			
Range	41 – 90	28 – 97	0.285*
Median (IQR)	70 (58 – 85)	78 (67 – 85)	NS
Serum ALT (u/l)			
Range	91 – 895	95 – 494	0.043*
Median (IQR)	287 (145 – 448)	196 (155 – 233)	S
Serum AST (u/l)			
Range	87 – 779	79 – 515	0.004*
Median (IQR)	256 (155 – 430)	170 (125 – 224)	S
Serum Total Bilirubin (mg/dl)			
Range	1.4 – 7.9	1.2 – 5.2	<0.001*
Median (IQR)	3.4 (2.4 – 4.2)	1.9 (1.6 – 2.7)	HS
Serum Creatinine (mg/dl)			
Range	1.5 – 6.3	1.4 – 3.8	0.105*
Median (IQR)	2 (1.8 – 2.3)	1.9 (1.8 – 2)	NS

IQR interquartile range [central 50% of ascendingly-ordered set of data]

[figure not shown]
Data presented as range, median (IQR); or number (percentage)

* Analysis using Mann-Whitney's U-Test

** Analysis using Chi-squared Test

[figure not shown]
NS non-significant – S significant – HS highly significant

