Table-11 Difference between Women who Died and Women who Survived regarding Schistocytes Percentage .

	Women who Died (n=3)	Women who Survived (n=97)	P
Schistocytes (%) Range	8.3 – 44	0 – 39	<0.001*
Median (IQR)	39 (8.3 – 44)	0.5 (0.1 – 1.1)	HS

[figure not shown]
IQR interquartile range [central 50% of ascendingly-ordered set of data]

Data presented as range, median (IQR)

* Analysis using Mann-Whitney's U-Test

[figure not shown]
HS highly significant

Figure-36 Box-Plot Chart showing Difference between Women who Died and Women who Survived regarding Schistocytes Percentage .

Receiver operator characteristic (ROC) curve was constructed for schistocytes percentage as a predictor of postpartum deterioration in included women. The curve showed a significant predictability as denoted by the significantly large area under the curve (AUC) (figure-37).

Figure-37 ROC Curve for Schistocytes Percentage as Predictor of Postpartum Deterioration in Included Women .

AUC = 0.883, 95% CI (0.770 to 0.996), $p < 0.001$

Table-15 shows the validity of schistocytes at different cutoff values as predictor of postpartum deterioration.

Table-12 Validity of Schistocytes as Predictor of Postpartum Deterioration in Included Women .

Schistocytes	Sensitivity	Specificity	PPV	NPV	FP	FN	LR+
$\geq 0.95\%$	88%	85.3%	66.7 %	95.5 %	14.7 %	12 %	6
$\geq 1.4\%$	84%	96%	87.5 %	94.7 %	4%	16 %	21
$\geq 1.9\%$	80%	98.7%	95.2 %	93.7 %	1.3%	20 %	60

[figure not shown]
PPV positive predictive value -NPV negative predictive value

FP false positive -FN false negative-LR+ positive likelihood ratio

ROC curves were constructed for initial clinical and laboratory data as predictors of postpartum deterioration. Among all measured variables, only initial ALT, initial AST and initial total bilirubin were significant predictors of postpartum deterioration. Their AUCs, though being significantly large, were smaller than the AUC for

schistocytes; indicating that the latter is a more significant and better predictor for postpartum deterioration (figure-38).

Figure-38 ROC Curves for Initial Clinical and Laboratory Data as Predictors of Postpartum Deterioration in Included Women .

Initial SBP: AUC = 0.441, 95% CI (0.324 to 0.559), p=0.381

Initial DBP: AUC = 0.404, 95% CI (0.283 to 0.525), p=0.152

Initial Hb Concentration: AUC = 0.479, 95% CI (0.341 to 0.616), p=0.750

Initial Platelet Count: AUC = 0.429, 95% CI (0.293 to 0.564), p=0.286

Initial ALT: AUC = 0.636, 95% CI (0.484 to 0.787), p=0.043

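### LDH is part of the HELLP entry criteria but appears in no result, so the statement that only three of all measured variables predicted deterioration is unsupported as worded

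*SAP*

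**What the plan says.** The protocol's inclusion criteria require that each woman "Fulfilled criteria for the diagnosis of HELLP syndrome". Its diagnostic criteria for HELLP syndrome use LDH twice: "Hemolysis documented by an increased LDH level and progressive anemia", and "Hepatic dysfunction documented by an LDH level >600 IU/L, elevated liver enzymes documented by AST >40 IU/L, ALT >40 IU/L, or both". The section on anticipating microangiopathic haemolytic anaemia, like the introduction, says that TTP-HUS should be considered in pregnant women with "severe thrombocytopenia, severe anemia, and elevated lactate dehydrogenase enzyme". The protocol's Laboratory test section lists the "complete blood count, using EDTA-anticoagulated peripheral blood sample, for concentration and platelet counts", followed by the smear; LDH is not listed there.

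The SAP document is the study's results chapter. Table-9 finds no significant difference "regarding the initial values of systolic blood pressure, diastolic blood pressure, albuminuria, hemoglobin concentration, platelet count or serum creatinine", and significant differences for ALT, AST and total bilirubin. The text introducing Figure-38 says that ROC curves were constructed for initial clinical and laboratory data and then states: "Among all measured variables, only initial ALT, initial AST and initial total bilirubin were significant predictors of postpartum deterioration". It goes on to conclude, from the smaller AUCs of those three, that schistocytes predict deterioration better.

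**The concern.** A variable that helps define eligibility should be available for every woman enrolled. LDH is also a marker that the protocol itself ties to haemolysis and to the condition the study hopes to anticipate. Its absence from every table and curve, with no reason given, does not fit a sentence that claims to cover everything measured.

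Two statements are at stake. One is that only three initial variables predicted deterioration. The other is that schistocytes are the better predictor, which a reader will take as a comparison with the routine laboratory work-up. The schistocyte results themselves (AUC 0.883 and Table-12) do not depend on LDH.

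**Working it through.** **1. Where LDH should appear, and where it does.**

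| Place in the SAP | Variables shown | LDH |
|---|---|---|
| Tables 5 and 9 (initial data) | 9: SBP, DBP, albuminuria, Hb, platelets, ALT, AST, bilirubin, creatinine | no |
| Table-6 (48 hours) | 8: the same without albuminuria | no |
| Figure-38 (ROC curves) | 8: the same without albuminuria | no |
| Table-13 (validity) | 3: ALT, AST, bilirubin | no |
| Table-15 (correlations) | 8: the same without albuminuria | no |

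The tables are legible, the AUCs are printed as text, and the captions of Figures 27 to 34 do not name LDH either. Lost figures do not explain the gap.

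**2. Reproducing the Figure-38 p-values.** Inputs: n1 = 25 deteriorated and n2 = 75 did not (Table-7), with the printed AUCs. The Mann-Whitney standard error under the null is sqrt((n1+n2+1)/(12·n1·n2)) = sqrt(101/22500) = 0.0670, and z = |AUC − 0.5|/0.0670.

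| Variable | AUC | p recomputed | p printed |
|---|---|---|---|
| SBP | 0.441 | 0.379 | 0.381 |
| DBP | 0.404 | 0.152 | 0.152 |
| Hb | 0.479 | 0.754 | 0.750 |
| Platelets | 0.429 | 0.289 | 0.286 |
| ALT | 0.636 | 0.042 | 0.043 |
| AST | 0.694 | 0.004 | 0.004 |
| Bilirubin | 0.772 | <0.001 | <0.001 |
| Creatinine | 0.607 | 0.110 | 0.110 |

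The printed figures are sound for the variables analysed.

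**3. How large an LDH AUC would contradict *only*?** 0.5 + 1.96 × 0.0670 = 0.631. This is just below the ALT value of 0.636, which the SAP counts as significant.

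**4. Albuminuria.** Table-9 gives the counts, so its AUC can be worked out (3+, 4+, 5+: 13, 5, 7 deteriorated; 28, 27, 20 did not). Counting ties as half, 13×14 + 5×(28+13.5) + 7×(55+10) = 182 + 207.5 + 455 = 844.5. Dividing by 25×75 = 1875 gives 0.450. Then z = 0.0496/0.0670 = 0.74 and p is about 0.46, or 0.43 with the tie correction. Its omission makes the wording inaccurate but does not change the list of three.

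**5. The lead over the best comparator shown.** Standard errors from the printed intervals: schistocytes (0.996 − 0.770)/3.92 = 0.0577; bilirubin (0.887 − 0.656)/3.92 = 0.0589. The difference is 0.883 − 0.772 = 0.111. Both AUCs come from the same women, so SE(diff) = sqrt(0.0577² + 0.0589² − 2r × 0.0577 × 0.0589). The correlation r is not reported and is assumed here.

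- r = 0: SE 0.082, z = 1.35, p = 0.18
- r = 0.3: SE 0.069, z = 1.61, p = 0.11
- r = 0.5: SE 0.058, z = 1.90, p = 0.06

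**6. Schistocytes against LDH, for assumed LDH AUCs only.** The LDH standard error uses the Hanley-McNeil formula with 25 and 75 women; r is again assumed.

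| Assumed LDH AUC | Difference | p at r = 0 | p at r = 0.5 |
|---|---|---|---|
| 0.70 | 0.183 | 0.034 | 0.003 |
| 0.75 | 0.133 | 0.114 | 0.025 |
| 0.80 | 0.083 | 0.31 | 0.15 |
| 0.85 | 0.033 | 0.67 | 0.55 |

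These rows show how much the comparison depends on the missing value. They are not an estimate of it.

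**The case against.** The strongest reply is that the documents never show an LDH result, a sampling time or a number measured, and the Laboratory test section does not list it. On that reading, the variables measured are simply those headed as initial clinical and laboratory data.

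Part of this stands. That a value exists for each woman is inferred from eligibility and is not confirmed. The Laboratory test list does not settle the matter, because ALT, AST, bilirubin and creatinine are missing from it too and yet are reported. If LDH was not measured in all women, eligibility is undocumented for those without it, and the report should say so. The narrower reading of the sentence also fails on its own terms, because albuminuria belongs to the initial data and has no curve.

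Other points stand as limits. Hb and bilirubin, which also bear on haemolysis, were analysed, so LDH is not the only such marker. The research question is whether schistocytes predict deterioration; no head-to-head comparison was planned. No paired AUC test is reported to which LDH could simply be added.

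A reader might infer that LDH would have matched or beaten schistocytes, or that leaving it out flattered them. The documents do not support this. No LDH value is given, and entry above 600 IU/L truncates its range, which may lower its AUC. That is a caveat for reporting it, not a reason for omitting it: entry criteria also restrict platelets and transaminases, and those were analysed.

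**Conclusion.** The point holds as a reporting and comparison gap. LDH is part of the entry criteria, is reported nowhere, and its absence is unexplained. The statement about all measured variables is unsupported as worded, and albuminuria shows the inaccuracy even without LDH. The claim that schistocytes predict better has not been tested against LDH, and no paired test supports it against bilirubin either (p about 0.18 to 0.06 for assumed correlations of 0 to 0.5).

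The size of any LDH effect is unknown. What can be said is that an AUC of about 0.631 or more would make LDH a fourth significant predictor. It would be too strong to say that the sentence is shown to be false in substance: that depends on LDH values that may not have been kept, and the derived albuminuria AUC of 0.450 leaves the list of three unchanged. The schistocyte AUC and cut-off table are unaffected.

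**What to change.** - Report initial LDH by group, with the number of women measured, in Tables 5 and 9, and 48-hour LDH in Table-6 if it was recorded.
- Add the LDH curve to Figure-38, and a row to Table-13 if LDH is a significant predictor. Note that entry above 600 IU/L truncates its range.
- Compare AUCs with a paired test such as DeLong's, for schistocytes against LDH and against bilirubin, with confidence intervals for the differences. Limit the claim of better prediction to what that test supports.
- If LDH values are not available, say so, and say how the LDH entry criterion was established.
- In either case, replace the reference to all measured variables with the list of variables analysed, and either add albuminuria or state that it was not put through ROC analysis.

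The wording change costs nothing. The rest is one more variable in existing analyses plus a paired test on data already held, provided that numeric LDH values were kept from eligibility.

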Figure-27 Box-Plot Chart showing Difference between Women who Deteriorated Postpartum and Women who did

not regarding Initial Systolic Blood Pressure .

Figure-28 Box-Plot Chart showing Difference between Women who Deteriorated Postpartum and Women who did

not regarding Initial Diastolic Blood Pressure .

Figure-29 Box-Plot Chart showing Difference between Women who Deteriorated Postpartum and Women who did not regarding Initial Hemoglobin Concentration .

[figure not shown]

Figure-30 Box-Plot Chart showing Difference between Women who Deteriorated Postpartum and Women who did not regarding Initial Platelet Count .

[figure not shown]
[figure not shown]

Figure-31 Box-Plot Chart showing Difference between Women who Deteriorated Postpartum and Women who did

not regarding Initial ALT .

Figure-32 Box-Plot Chart showing Difference between Women who Deteriorated Postpartum and Women who did not regarding Initial AST .

[figure not shown]

Figure-33 Box-Plot Chart showing Difference between Women who Deteriorated Postpartum and Women who did not regarding Initial Serum Total Bilirubin .

Association between the Quantitative Assessment of Schistocytes in Peripheral Blood Smear and Prognosis of Patient Initially Diagnosed as HELLP Syndrome (Study results)

[figure not shown]
[figure not shown]

Figure-34 Box-Plot Chart showing Difference between Women who Deteriorated Postpartum and Women who did

not regarding Initial Serum Creatinine .

The median schistocytes percentage was significantly higher in women who showed postpartum deterioration, when compared to women who did not deteriorate (table-10, figure-35).

Table-10 Difference between Women who Deteriorated Postpartum and Women who did not regarding Schistocytes Percentage .

	Women who Deteriorated Postpartum (n=25)	Women who Did not Deteriorate Postpartum (n=75)	P
Schistocytes (%)			
Range	0 – 44	0 – 6	<0.001*
Median (IQR)	5.5 (2 – 8.4)	0.5 (0.05 – 0.7)	HS

[figure not shown]
IQR interquartile range [central 50% of ascendingly-ordered set of data]

Data presented as range, median (IQR)

* Analysis using Mann-Whitney's U-Test

HS highly significant

Figure-35 Box-Plot Chart showing Difference between Women who Deteriorated Postpartum and Women who did

not regarding Schistocytes Percentage .

The median schistocytes percentage was significantly higher in women who died when compared to women who survived (table-11, figure-36).

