Initial AST: AUC = 0.694, 95% CI (0.553 to 0.834), p=0.004

Initial Serum Total Bilirubin: AUC = 0.772, 95% CI (0.656 to 0.887), p=<0.001

Initial Serum Creatinine: AUC = 0.607, 95% CI (0.468 to 0.746), p=0.110

Table-13 shows the validity of initial values of ALT, AST, and total bilirubin as predictors of postpartum deterioration. Again, the validity parameters were remarkably lower than the corresponding parameters of schistocytes.

Table-13 The validity of initial values of ALT, AST, and total bilirubin as predictors of postpartum deterioration.

	Sensitivity	Specificity	PPV	NPV	FP	FN	LR⁺
Initial ALT ≥ 230 u/L	60%	72%	41.7 %	84.4 %	28%	40%	2.1
Initial AST ≥ 240 u/L	60%	84%	55.6 %	86.3 %	16%	40%	3.8
Initial Total Bilirubin ≥ 2.95 mg/dl	68%	81.3%	54.8 %	88.4 %	18.7 %	32%	3.6

ALT alanine transaminase - AST aspartate transaminase

PPV positive predictive value -NPV negative predictive value

[figure not shown]
FP false positive -FN false negative

LR+ positive likelihood ratio

ROC curve was constructed for schistocytes percentage as a predictor of maternal mortality in included women. The curve showed a significant predictability as denoted by the significantly large area under the curve (AUC) (figure-39).

Figure-39 ROC Curve for Schistocytes Percentage as Predictor of Maternal Mortality in Included Women .

Association between the Quantitative Assessment of Schistocytes in Peripheral Blood Smear and Prognosis of Patient Initially Diagnosed as HELLP Syndrome (Study results)

$AUC = 0.985, 95\% CI (0.956 \text{ to } 1.103), p=0.004$

Table-14 shows the validity of schistocytes as predictor of maternal mortality in included women.

Table-14 Validity of Schistocytes as Predictor of Maternal Mortality in Included Women .

Schistocytes	Sensitivity	Specificity	PPV	NPV	FP	FN	LR+
≥ 8.2%	100%	95.9%	42.9%	100%	4.1%	0%	24.3

PPV positive predictive value

NPV negative predictive value

FP false positive

FN false negative

LR+ positive likelihood ratio

There were significant positive correlations between schistocytes percentage and each of systolic and diastolic blood pressures, serum ALT, serum AST, serum total bilirubin and serum creatinine 48 hours postpartum. There were significant negative correlations between schistocytes and each of hemoglobin concentration and platelet count 48 hours postpartum (table-15, figures 40-43).

Table-15 Correlation between Schistocytes and Both Clinical and Laboratory Data 48 hours Postpartum in Included Women .

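### Schistocytes are declared a better predictor than initial bilirubin, AST and ALT with no paired comparison of AUCs; against bilirubin the printed figures leave superiority in AUC undetermined

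*SAP*

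**What the plan says.** In the SAP's Results, Figure-37 gives the schistocyte result for postpartum deterioration as "AUC = 0.883, 95% CI (0.770 to 0.996"), with p<0.001. Figure-38 gives the comparators:

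- "Initial Serum Total Bilirubin: AUC = 0.772, 95% CI (0.656 to 0.887), p=<0.001"
- "Initial AST: AUC = 0.694, 95% CI (0.553 to 0.834), p=0.004"
- "Initial ALT: AUC = 0.636, 95% CI (0.484 to 0.787), p=0.043"

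The text above Figure-38 notes that these three AUCs are smaller than that of "schistocytes; indicating that the latter is a more significant and better predictor for postpartum deterioration (figure-38"). No other basis is given for the ranking.

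A second comparative statement introduces Table-13, which shows one cutoff each for ALT, AST and bilirubin: "Again, the validity parameters were remarkably lower than the corresponding parameters of schistocytes". Table-12 gives three cutoffs for schistocytes (≥0.95%, ≥1.4%, ≥1.9%). Neither table has intervals, and the supplied documents do not say how any cutoff was chosen.

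**The concern.** Two AUCs from the same women are correlated estimates. To say that one marker is better, the difference has to be estimated with its own standard error, which depends on that correlation. Ranking the point estimates does not do this.

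Ranking the p values does not do it either. Each p value asks whether one marker discriminates at all, so a smaller p is not evidence that one marker beats another. Here even that ranking fails for bilirubin, because both p values are printed only as below 0.001.

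The sentence is a stated conclusion about relative predictive value, and bilirubin is already among the initial laboratory data. A reader would take the added value of the smear count over bilirubin as demonstrated.

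**Working it through.** **Inputs.** 25 women deteriorated and 75 did not (Table-7). AUCs and CIs are from Figures 37 and 38, and sensitivities and specificities from Tables 12 and 13. The correlation r between AUC estimates is not given, so it is varied as an assumption. The Spearman coefficient of 0.313 in Table-15 does not supply it, because it concerns bilirubin at 48 hours, not initial bilirubin. A two-sided 0.05 level is assumed.

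**1. What the printed p values test.** Under no discrimination, the SE of an AUC is √[(n₁+n₀+1)/(12·n₁·n₀)] = √[101/(12·25·75)] = 0.0670. With z = (AUC − 0.5)/0.0670:

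| Marker | z | p | Printed p |
|---|---|---|---|
| ALT | 0.136/0.0670 = 2.03 | 0.042 | 0.043 |
| AST | 0.194/0.0670 = 2.90 | 0.0038 | 0.004 |
| Bilirubin | 0.272/0.0670 = 4.06 | 0.00005 | <0.001 |

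The printed values are reproduced to within rounding. The ALT and AST values also equal those in Table-9, whose footnote reads "Analysis using Mann-Whitney's U-Test". They are single-marker tests against 0.5.

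**2. Standard errors from the printed CIs**, as width/(2 × 1.96):

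- schistocytes: (0.996 − 0.770)/3.92 = 0.0577
- bilirubin: (0.887 − 0.656)/3.92 = 0.0589
- AST: (0.834 − 0.553)/3.92 = 0.0717
- ALT: (0.787 − 0.484)/3.92 = 0.0773

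**3. Schistocytes minus bilirubin.** The difference is 0.111, with SE = √(s₁² + s₂² − 2·r·s₁·s₂).

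| r (assumed) | SE | 95% CI | p |
|---|---|---|---|
| 0 | 0.0824 | −0.051 to 0.273 | 0.18 |
| 0.3 | 0.0690 | −0.024 to 0.246 | 0.11 |
| 0.5 | 0.0583 | −0.003 to 0.225 | 0.057 |
| 0.6 | 0.0522 | 0.009 to 0.213 | 0.033 |
| 0.8 | 0.0369 | 0.039 to 0.183 | 0.003 |

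Setting 0.111/SE = 1.96 and solving gives r = 0.53 (0.52 to 0.54 allowing for rounding of the inputs). With Hanley-McNeil SEs instead (0.0459 and 0.0595) the threshold is about 0.45. If the three comparisons were Bonferroni-adjusted (critical value 2.394), it would be about 0.68.

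**4. Schistocytes minus AST and ALT.**

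- AST: difference 0.883 − 0.694 = 0.189. At r = 0 the SE is 0.0920, CI 0.009 to 0.369, p = 0.040. With Bonferroni it would need r above about 0.27.
- ALT: difference 0.883 − 0.636 = 0.247. At r = 0 the SE is 0.0964, CI 0.058 to 0.436, p = 0.010, which is below 0.05/3 = 0.0167.

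**5. The cutoff comparison with bilirubin.** The percentages convert to whole counts that reproduce the printed PPV and NPV. Bilirubin ≥2.95 mg/dl detects 17/25 and correctly excludes 61/75. The overlap between tests is not reported, so the exact McNemar p was computed for every possible overlap:

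| Schistocytes | Sensitivity | p range | Specificity | p range |
|---|---|---|---|---|
| ≥0.95% | 22/25 | 0.06–0.23 | 64/75 | 0.25–0.69 |
| ≥1.4% | 21/25 | 0.13–0.39 | 72/75 | 0.001–0.013 |
| ≥1.9% | 20/25 | 0.25–0.58 | 74/75 | 0.0002–0.001 |

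Specificity favours schistocytes at the two higher cutoffs whatever the overlap. Sensitivity is not clearly different at any cutoff, and neither measure is at ≥0.95%.

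**The case against.** The strongest reply is that the AUC is not the only evidence. Counting all misclassified women at the printed cutoffs, schistocytes ≥1.4% make 4 + 3 = 7 errors and bilirubin makes 8 + 14 = 22. The exact McNemar p is at most 0.008 under every possible overlap. At ≥1.9% there are 5 + 1 = 6 errors and p is at most 0.004. This is correct, and it means that *undetermined* should be read as applying to the AUC. It still does not establish superiority. Three schistocyte cutoffs are set against one for bilirubin, no selection rule is stated, and performance is assessed in the same women. At ≥0.95% (14 against 22 errors) p runs from 0.008 to 0.24 depending on the overlap.

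It can also be said that this is one sentence in a pilot study whose question is whether schistocytes predict deterioration, not whether they beat bilirubin. That limits the consequence, but the comparative conclusion is still drawn, and a small sample makes an untested ranking less secure.

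Two further points stand. Neither document requires a Bonferroni correction, so those thresholds are only a sensitivity check. The supplied SAP opens at the Results chapter, so a cutoff rule can only be said to be absent from the documents supplied.

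**Conclusion.** The concern holds. The claim that schistocytes are the more significant predictor is not a comparison of markers. The claim that they are better was not tested against any of the three.

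Against bilirubin, a difference of 0.111 reaches p<0.05 only if the two AUC estimates correlate above about 0.53. The point estimate favours schistocytes, but the printed figures neither show nor refute superiority in AUC. Against ALT, and nominally AST, a paired test would probably support the ordering; there the fault is the missing test, not a doubtful result.

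This rests on symmetric normal-theory CIs for the AUCs and on the assumed range of r. The protocol's question, the schistocyte AUC of 0.883 and the group difference in Table-10 (p<0.001) are unaffected.

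**What to change.** - Report the paired AUC difference (DeLong or paired bootstrap) with its 95% CI for schistocytes against each of bilirubin, AST and ALT, and say whether multiplicity was addressed.
- Call schistocytes better only where the CI excludes zero; otherwise say that the AUC was numerically larger. Delete the statement about greater significance.
- For Table-12 against Table-13, state how the cutoffs were chosen and add 95% CIs, or label the comparison as descriptive.
- Optional and exploratory only: a model with bilirubin plus schistocytes. It needs a transformation defined at zero, such as log(1 + schistocyte %), because the ranges in "Table-10 Difference between Women who Deteriorated Postpartum and Women who did not regarding Schistocytes Percentage" start at 0 in both groups.

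The cost is one small analysis of data already collected and a reworded sentence. The claim over bilirubin may have to be softened.
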